6.10 Analysis Plan

Main Study: All analyses will be conducted on an intention-to-treat basis, with the caveat that infants surviving to discharge, but lost to follow-up at 22-26 months, will be excluded from the primary analysis and considered ignorably missing. We will, however, assess the impact of outcomes lost to follow-up on our results by performing sensitivity analyses that assume all positive or all negative outcomes for those with missing data. We will also conduct bivariate analyses to compare the in-hospital characteristics of children lost to follow-up versus those with assessment of the primary outcome. Note that, based on previous NRN trials in similar populations, we expect the follow-up rate among survivors to be above 90%.

All analyses will be adjusted for design effects: stratification by center and birth weight group. The primary outcome of death or NDI at 22-26 months adjusted age will be analyzed using robust Poisson regression. Adjusted relative risks and 95% confidence intervals will be reported. Secondary analyses of the primary outcome may adjust for additional baseline covariates such as SNAPPE scores at NICU admission and socioeconomic status..

The consistency of the treatment effect over birth weight strata and gender, and treatment heterogeneity across the different centers, will be investigated.

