Sample size will be based on power considerations for the parent clinical trial. All analyses will utilize an intention-to-treat approach. Data confirmed to be missing at random will be addressed as appropriate using multiple imputation.⁹⁷ We will first directly compare mean cost between the study groups using generalized linear modeling to account for the typically right skewed cost data distribution.^{98,99} We will then calculate the incremental cost-effectiveness ratio, defined as the difference in mean cost per patient in the high and low transfusion threshold arms divided by the difference in the mean effect between the study arms. The outcome will thus be expressed as the cost per survivor without neurodevelopmental impairment. To assess statistical uncertainty in the joint distribution of costs and effects, we will use nonparametric bootstrapping and report results as cost-effectiveness acceptability curves.^{100,101,102,103} Finally, we will assess uncertainty in parameter values by using sensitivity analysis, in which we will recalculate the cost-effectiveness after varying the input values for certain variables through a plausible range.

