4.0 Specific Aims

4.1 Specific Aim 1

To examine whether the clinically relevant composite primary outcome of death or significant neurodevelopmental impairment in survivors at 22-26 months of corrected age is less common among preterm infants who, by transfusion practice, are maintained at higher hemoglobins. Neurodevelopmental assessments will be performed by trained and annually recertified examiners, who are masked to treatment allocation, using standardized tools: the Bayley Scales of Infant Development-III (BSID-III) and the Gross Motor Function Classification Scale (GMFCS).^{125,126} The primary outcome consists of any one of the following: (i) Cognitive delay where delay is defined as BSID-III cognitive score < 85 (>1 standard deviation below the mean). (ii) Cerebral Palsy if the child has a non-progressive motor impairment characterized by abnormal muscle tone and impaired range or control of movements. Moderate cerebral palsy (CP) is defined as level II or III on the GMFCS. Severe or non-ambulatory CP consists of GMFCS IV or V. (iii) Severe vision impairment, defined as corrected visual acuity in the better eye less than 20/200, determined by pediatric ophthalmologists. (iv) Severe hearing impairment, defined as bilateral hearing loss requiring amplification or cochlear implant. (v) Death before 22-26 month follow-up assessment. The primary outcome is deemed present if one or more of the individual components of the composite outcome are present, or absent if no component was present. If no component is present, one or more missing components render the primary outcome to be deemed missing.

4.2 Specific Aim 2

We will examine in which arm the following secondary outcomes are more common:

Short term, to NICU discharge:

- (a) Survival to discharge without severe morbidity, defined as any of the following: bronchopulmonary dysplasia, retinopathy of prematurity (stage ≥ 3 or requiring treatment), or serious brain abnormality (grade 3 or 4 intraventricular hemorrhage, periventricular leukomalacia, or ventriculomegaly).
- (b) Weight, length, and head circumference at 36 weeks postmenstrual age or at discharge from NICU, whichever occurs first.
- (c) Serious abnormality on cranial ultrasound examination: grade 3 or 4 intraventricular hemorrhage, periventricular leukomalacia, or ventriculomegaly;
- (d) Age at final tracheal extubation; age at final caffeine dose

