6.4 Prevention of Bias in an Unblinded Trial

All eligible infants of ≤ 1000 g birth weight and gestational age 22 0/7 through 28 6/7 weeks will be screened and logged, reducing selection bias. Randomization will be concealed, preventing allocation bias. It is impossible practically or ethically to blind either the caregivers or parents to the assigned hemoglobin threshold. Interim results will be presented to the Data Safety and Monitoring Committee (DSMC) with treatment assignments labeled only as group “A” or “B”. We will record all hemoglobin measures and transfusions given in order to assess protocol compliance. Site investigators will review compliance with clinicians at the onset of the trial and thereafter monthly as appropriate. Examiners at the 22-26 month examination will be unaware of treatment assignment, as will the radiologists interpreting the brain ultrasounds. Within NRN centers, local site interpretations were highly accurate and inter-rater reliability was excellent for the diagnosis of grade 3 or 4 IVH.¹³⁶

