6.6 Choice of Primary Outcome

We will use a composite outcome of death or significant neurodevelopmental impairment in survivors at 22-26 months of corrected age. Children will be assessed at 22-26 months of corrected age by staff unaware of assignment. Centers will schedule visits as early as possible within this window. Outcome assessments will be conducted by physicians or nurses specializing in neonatal follow-up examination and certified psychologists. Neurodevelopmental Impairment will be defined in this study, as one or more of the following: cognitive delay, moderate or severe cerebral palsy, or severe visual or hearing impairment, as defined below.

Cognitive delay will be assessed by certified psychologists will assess infants using the Bayley Scales of Infant Development III (BSID-III). Cognitive delay is defined as BSID-III cognitive score < 85 (>1 standard deviation below the mean).

Cerebral Palsy is diagnosed if the child has a non-progressive motor impairment characterized by abnormal muscle tone and impaired range or control of movements. Medical history, physical examination and neurological examinations will be used to determine the presence of moderate or severe cerebral palsy (CP). Moderate CP is defined as level II or III on the Gross Motor Function Classification Scale (GMFCS).^{125,126} Severe or non-ambulatory CP consists of GMFCS IV or V.

Severe vision impairment; is defined as corrected visual acuity in the better eye less than 20/200 determined by pediatric ophthalmologists.

Severe hearing impairment, is defined as bilateral hearing loss requiring amplification or the insertion of a cochlear implant as determined by a sound field hearing assessment or auditory brainstem responses.

The primary outcome will be deemed present if one or more of the individual components of the composite outcome are known to be present, or absent if no component was present. If no component was present, one or more missing components will cause the primary outcome to be deemed missing.

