6.9 Statistical Design Considerations

The primary objective of the TOP trial is to assess the difference in the primary outcome of survival without significant NDI (or, equivalently, death or NDI) at 22-26 months adjusted age in the two treatment arms. This outcome is similar to that used in the PINT trial, which found rates of death or neurosensory impairment at 18 months of 45.2% in the low trigger group and 38.5% in the high trigger group. Based on these findings, we believe that an absolute difference of 7% is the minimal clinically significant difference we would wish to detect in the rate of death or NDI. We considered several other factors in estimating the sample size for this study. First, we calculated the rate of death or NDI among infants born at NRN centers in 2005-2008 with GA 22-26 weeks and birth weight <1000 g who survived to 12 hours, which was 52%. However, we recognized that this population differed somewhat from that of the TOP trial, which proposes to enroll infants less than 29 weeks GA. In addition, the current NRN definition of NDI incorporates only the cognitive composite score of the Bayley III, while future definitions will likely also involve the Bayley III motor scales which have been collected in the Network only since January 2010. Thus, we recognized the limitations of estimating our sample size based only on current NRN data. At the same time, however, we were aware that the most conservative sample size estimate would result from an event rate of 50%, which current NRN data indicated was not implausible in our population. This led us to choose a conservative estimate based on assumed outcome rates of 53.5% and 46.5% (i.e., centered around an overall event rate of 50%) in the two treatment groups. With a two-tailed alpha of 0.05 and 80% power, the initial sample size estimate was 1,658 infants. The sample size was additionally inflated by 10% to account for loss to follow up at 22-26 months, yielding a final sample size estimate of 1,824.

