Although the sample size calculations described above were based on the primary outcome, we will have 80% power with a two-tailed alpha of 0.05 to detect the following differences in important secondary outcomes (rates in the low threshold group are based on findings of the PINT trial): any transfusion 89.0% in the low threshold group (LOW) vs. 92.9% in the high group (HI); NEC 8.5% in LOW vs. 5.0% in HI; brain injury (PVL, echodense lesions or ventriculomegaly) on latest ultrasound (US) or neuroimaging closest to 36 weeks 18.5% in LOW vs. 24.6% in HI; death before discharge 21.5% in LOW vs. 16.1% in HI; combined death, severe ROP, BPD, or US brain injury 74.0% in LOW vs. 67.7% in HI.

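### With similar loss in both arms, the two planned missing-outcome analyses cannot show how the result would change if lost children fared differently by arm.

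*Combined protocol and SAP*

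**What the plan says.** Section 6.10 leaves children who survived to discharge but were lost by 22-26 months out of the primary analysis and treats their absence as ignorable. Appendix A section 6 repeats the exclusion. Both test its effect on the result by "sensitivity analyses that assume all positive or all negative outcomes for those with missing data". Both also plan a comparison of in-hospital characteristics between lost and assessed children. That comparison is not stated to be by arm and does not re-estimate the treatment effect.

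The set of missing outcomes is wider than children not seen. Section 6.6 adds: "If no component was present, one or more missing components will cause the primary outcome to be deemed missing". Section 4.1 has the same rule: "If no component is present, one or more missing components render the primary outcome to be deemed missing".

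Multiple imputation is mentioned only for the economic evaluation in section 3.2: "Data confirmed to be missing at random will be addressed as appropriate using multiple imputation". For the primary outcome, no analysis in the documents gives missing children different event rates by arm.

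On the expected amount of loss, section 6.10 says "we expect the follow-up rate among survivors to be above 90" per cent.

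**The concern.** Treating missing outcomes as ignorable is the assumption that the sensitivity analyses should stress. For a comparison of two arms, the departure that matters most is that lost children do differently in one arm than in the other. A single value for all missing children sets that difference to zero in both planned analyses. Two significant sensitivity results could then be read as evidence that the finding is robust to loss, although this departure was never examined. The question is most practical for a significant result somewhat below the target, which section 6.9 describes thus: "an absolute difference of 7% is the minimal clinically significant difference we would wish to detect in the rate of death or NDI".

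**Working it through.** **The plan's own figure.** Two proportions, 53.5% vs 46.5%, two-sided alpha 0.05, 80% power, with continuity correction: 829 per arm, so 1,658. Then 1,658 × 1.10 = 1,824, or 912 per arm. Both figures in section 6.9 reproduce.

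**Why the pair moves so little.** Let a fraction f be missing in each arm, with complete-case rates pL and pH.
- All negative: rates become (1−f)pL and (1−f)pH. The relative risk is unchanged.
- All positive: rates become (1−f)p + f. The relative risk moves slightly towards 1.
- In both, the risk difference is (1−f) times the observed one. Its sign cannot change.

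**Inputs for the illustration.**
- 912 per arm (section 6.9; 1:1 allocation in section 7.1).
- Mortality d, from section 6.9: "death before discharge 21.5% in LOW vs. 16.1% in HI". The low-threshold (LOW) rate comes from the PINT trial. The high-threshold (HI) rate is a detectable value, not a forecast.
- Loss l = 10% of survivors in each arm (assumption; the outer edge of expected follow-up). Also 8% and 5%.
- Full-cohort event rates p (assumption): (a) 53.5% vs 46.5%, (b) 53.0% vs 47.0%, (c) 52.7% vs 47.3%.

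**Formulas.** Survivors S = 912(1−d). Lost = l × S. Neurodevelopmental impairment (NDI) in survivors s = (p−d)/(1−d). Observed events = 912d + (S − lost) × s. Tests are pooled two-proportion z-tests.

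**Case (a) in full.** LOW: S = 715.9, lost 71.6, s = 32.0/78.5 = 40.8%, observed events 458.7 of 840.4 (54.6%). HI: S = 765.2, lost 76.5, s = 30.4/83.9 = 36.2%, observed events 396.4 of 835.5 (47.4%). Complete-case difference 7.1 points, relative risk (RR) 0.87.
- All positive: 530.3 vs 472.9 of 912, RR 0.89, p=0.007.
- All negative: 458.7 vs 396.4 of 912, RR 0.86, p=0.003.
- Tipping point: keep lost LOW survivors at 40.8%, so LOW has 487.9 events. p reaches 0.05 when the difference falls to 4.59 points, that is 446.1 HI events. This needs (446.1 − 396.4)/76.5 = 65.0% NDI among lost HI survivors, a gap of 65.0 − 40.8 = 24.2 points.

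**All three cases at 10% loss.**

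| Case | Complete-case difference | All positive p | All negative p | NDI in lost HI at tipping point | Gap, lost HI minus lost LOW |
|---|---|---|---|---|---|
| (a) | 7.1 | 0.007 | 0.003 | 65% | 24 points |
| (b) | 6.2 | 0.021 | 0.011 | 54% | 13.5 points |
| (c) | 5.6 | 0.037 | 0.021 | 47% | 7 points |

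The complete-case differences exceed the full-cohort ones (7.0, 6.0 and 5.4) because deaths are never missing.

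**Range over loss.** The gaps for (a), (b) and (c) are about 31, 18 and 10 points at 8% loss, and 53, 30 and 17 at 5%.

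**Other checks.**
- Other mortality assumptions (21.5% vs 17.5%; 12% in both arms; 21.5% in both arms) put the tipping rates in lost HI survivors at 63-67%, 50-56% and 43-49%.
- An unadjusted robust Poisson test changes the tipping rate by 0.002 or less.
- Crossed extremes in case (a), with all missing positive in one arm and none in the other, give RR 1.03 and 0.75.
- Unequal loss is picked up: in case (a) with 6% LOW and 10% HI lost, all positive gives p=0.057.
- If 20% of missing HI survivors were part-assessed and unimpaired (assumption), the wholly lost would need 65.0/0.8 = 81%, 67% and 59%. The component rule could therefore make the result less fragile.

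**The case against.** The strongest reply is that these tipping points mostly measure distance from p=0.05. The extra HI events needed are about 22, 13 and 7 in cases (a), (b) and (c), and they are the same at 5%, 8% and 10% loss. At the tipping point the difference is still about 4.6 points in favour of HI. This stands, and it is why a grid should show estimates and intervals, not only where significance goes.

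The inputs also sit at an edge. Ten per cent is the most loss that the plan expects, and the assumed mortality gap (21.5 − 16.1 = 5.4 points) accounts for the whole full-cohort difference in case (c). This stands too; the ranges above allow for it.

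The plan has other safeguards: the lost-versus-assessed comparison, optional adjustment for illness severity and socioeconomic status, and monitoring of retention by the safety committee. None re-estimates the effect with arm-specific missing outcomes. The wording does not expressly forbid arm-specific filling, and Appendix A lists development of a statistical analysis plan among the coordinating center's procedures. If more is intended, the text should say so.

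A reader might go further and infer that the primary estimate is biased, or that loss will depend on arm because families know the allocation: "It is impossible practically or ethically to blind either the caregivers or parents to the assigned hemoglobin threshold". The documents do not support that. The algorithm ends at 36 weeks postmenstrual age or NICU discharge (section 6.2), families unlikely to return are excluded (6.1), follow-up examiners are masked (6.4), and earlier network trials assessed over 90% (7.2).

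**Conclusion.** The gap in the plan is real but limited. With similar loss by arm, the planned pair cannot test whether lost children fared differently by arm, and nothing else in the documents does so for the primary outcome. A result at the 7-point design effect is fairly robust: a gap of about 24 points among lost survivors is needed at 10% loss, and more at lower loss. For complete-case differences of about 6.2 and 5.6 points, gaps of about 13.5 and 7 points suffice while both planned analyses stay significant.

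These values are illustrative. They rest on the mortality and loss assumptions stated, equal loss by arm, lost LOW survivors at the rate of those assessed, and nominal p<0.05. Center and birth-weight adjustment, correlation of multiple births and interim alpha spending are not modelled. The reading of the plan and the arithmetic are secure; how likely such gaps are cannot be judged from the documents. This is a worthwhile, cheap improvement, not an error in the plan.

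**What to change.** In section 6.10 and Appendix A section 6:
- Keep the two planned analyses.
- Add a prespecified grid, fitted with the primary model, that varies the event rate of children with missing outcomes separately in each arm.
- Report the relative risk and 95% confidence interval across the grid as well as the point where significance is lost.
- Show the two crossed extremes, labelled as implausible outer bounds.
- Report children missing under the component rule of sections 4.1 and 6.6 separately from children not seen at all.

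Cost: plan wording and slightly more programming, with no new data or patients. The drawback is that the crossed extremes will look unfavourable, so the label matters. The grid also documents robustness where it exists.

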Economic Evaluation: We will conduct a formal, prospective economic evaluation with patient-level cost and efficacy data, using standard methods used in similar multicenter trials (56-60). Medical expenditure data from hospitals and families will be collected. The analysis will first directly compare mean costs between the two treatment groups using generalized linear modeling to account for the typically right-skewed cost data distribution. We will then calculate the incremental cost-effectiveness ratio, defined as the difference in mean cost per patient in the two groups, divided by the difference in the mean effect between the study arms. The outcome will thus be expressed as the cost per survivor free of significant NDI. To assess statistical uncertainty in the joint distribution of costs and effects, we will use nonparametric bootstrapping and report results as cost-effectiveness acceptability curves. Finally, we will assess uncertainty in parameter values by using sensitivity analysis, in which we will recalculate the cost-effectiveness after varying the input values for certain variables through a plausible range. Further details are provided in the fuller protocol.

6.11 Data and Information Management

The data management system (DMS) recommended for the TOP study is a general purpose distributed data entry and management system developed to enable clinics to enter data from medical record extractions or other sources. This table-driven system is designed in a way that allows quick implementation of new studies into the existing system. Versions of this system, continually updated, have been successfully used for data collection for all NRN studies since 1998. An expanded version of this section is contained in the 'Data Safety and Monitoring Plan' (**Appendix A**).

7.0 Methods

7.1 Randomization Method

Eligible infants whose parents consent to enrollment will be randomized to the high or low threshold group. Permuted block randomization with randomly chosen block sizes of two and four will be performed. The allocation ratio will be 1:1 and infants will be stratified by study center and birth weight (<750 g versus 750-999 g). Multiple births, which are common in this premature population (comprising 26% of infants <29 weeks gestational age in the 2009 NRN Generic Data Base), will be randomized independently. The study allocation (low or high threshold) will be randomly assigned to each patient number (to be assigned to enrolled patients sequentially within each center), in advance, using a computer-based random number generator. Study personnel at each center will telephone a secure automated toll-free line at RTI to obtain the randomized assignment for each enrolled patient. Back-up personnel at RTI will be in place in case of failure of the automated system, to ensure 24/7/365 randomization. Details of interaction of RTI with study sites, and clinical case record forms (CRFs) are provided in the Manual of Procedures (MOP).

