3.3.6 How this Trial will Deal with These Possible Confounders

We will randomize 1824 infants and examine the primary outcome of death or neurodevelopmental impairment at 22-26 months. Given our large, generalizable, pragmatic trial design, we cannot mandate local laboratory practices to adopt uniform blood banking practices. Instead we have adopted the following strategy:

- i. We have appointed a 'TOP Trial Blood Banking Committee' led by [name] as Chair. Members were selected for expertise in blood banking practices. They will conduct a survey of all the blood banks by site to ensure that practices fall within an acceptable range for standards of care. Before the study begins, we will conduct a survey on pertinent blood bank practices in the 18 participating sites of the NRN. This will be the subject of a separate report and will inform the TOP trial of the likely magnitude of variation among the sites.
- ii. Patients will be stratified by center, and analyses will adjust for center.

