6.0 Study Design

6.1 Study Population, Inclusion and Exclusion Criteria, Withdrawals

Inclusion criteria: Infants – inborn or outborn – who are admitted to participating NICUs and who fulfill the following inclusion criteria are eligible for enrollment: (a) Birth weight ≤ 1000 g and gestational age at least 22 weeks but less than 29 weeks; and (b) Less than 48 hours of age.

Exclusion criteria: Infants meeting any of the following criteria will not be eligible: (a) Considered nonviable by the attending neonatologist. (b) Cyanotic congenital heart disease. (c) Parents opposed to the transfusion of blood. (d) Parents with hemoglobinopathy or congenital anemia. (e) *In-utero* fetal transfusion. (f) Twin-to-twin transfusion syndrome. (g) Isoimmune hemolytic disease. (h) Lack of parental consent. (i) Prior blood transfusion on clinical grounds beyond the first 6 hours of life. (j) High probability that the family is unable to return for the follow-up assessment at 22-26 months. (k) Infant has received erythropoietin prior to randomization, or is intended to receive erythropoietin through the neonatal course. (l) Congenital condition, other than premature birth, that adversely affects life expectancy or neurodevelopment.

Algorithm Deviations: Infants who by either late diagnosis or clinical deterioration are found to have conditions listed in the exclusions will be transfused according to the preference of their medical team rather than by study protocol. However, their outcomes will be measured and analyzed according to original allocation by intention-to-treat principles.

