6.3 Stratification, Random Allocation, and Enrollment Procedure

Parents of eligible infants who conform to the inclusion and exclusion criteria will be approached by the clinical study team (either a research nurse coordinator or a physician investigator) within 48 hours of birth in order to offer study participation. A log will be maintained of all screened infants indicating which are eligible and which were enrolled. On receipt of consent, treatment assignment (high or low transfusion threshold group) will be made using a telephone system of randomization by the Data Coordinating Center (RTI International). Randomization will be performed within the appropriate birthweight and center stratum. Detailed instructions for treatment allocation and implementation and monitoring of the study protocol will be given to the research nurse and to on-call physicians in each participating center.

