7.2 Recruitment and Enrollment Plans

The NRN, with its 18 large academic medical centers, several with large satellite sites of their own, is uniquely positioned to successfully complete this rather large and ambitious neonatal trial. The trial poses an important and unresolved question in neonatal medicine, and both the PINT and Iowa trials indicate collective equipoise and high consent rates (>70%). Moreover, NRN centers have demonstrated the ability to recruit and randomize patients at all hours in previous studies where time was an important factor, and have an impressive track record in following infants through 18-22 months of age.. The NRN has achieved > 90% outcome assessment at 18-22 months follow-up in each of its previous trials. The most recent examples are the Phototherapy and Hypothermia trials, where >91% subjects had primary outcomes at 18-22 months and 6-7 years of age, respectively (47,50). In Table 8, below we provide different scenarios on the recruitment timeline for the TOP trial, based on most recent numbers from the NRN Generic Database. It demonstrates that this trial can indeed be successfully completed by the NRN centers within the requested funding period.

Table 8 Enrollment Timeline for the TOP Trial

Predicted GDB Enrollment Per Month	Percent		Recruited Per Month (per center)	Estimated Total Time to Enroll
	Consent Rate	Unable to Recruit for Other Reasons		
152	70	10	91 (5.7)	20 months
152	60	10	76 (4.7)	24 months
152	50	10	60 (3.8)	30 months

Similar to other NRN trials, recruitment will be monitored closely by the DCC through regular enrollment reports, and low enrollment at a center will prompt the CCC, DCC, NIH, and

other members of the trial subcommittee to hold conference calls with such centers to identify problems and develop solutions.

Although the acute enrollment is envisaged to be for 30 months, the follow-up phase will be longer. Our window for the follow-up is centered on 24 months, and extends from 22 to 26 months.

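### Printed block sizes of two and four, in an open trial stratified by centre and birth weight, leave about one assignment in ten predictable and weaken the concealment described in section 6.4

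*Combined protocol and SAP*

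**What the plan says.** Section 7.1 of the protocol fixes the method: "Permuted block randomization with randomly chosen block sizes of two and four will be performed". It goes on: "The allocation ratio will be 1:1 and infants will be stratified by study center and birth weight (<750 g versus 750-999 g". Section 6.3 confirms where the blocks run: "Randomization will be performed within the appropriate birthweight and center stratum".

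Section 6.4 accepts that the treating team will know the arm: "It is impossible practically or ethically to blind either the caregivers or parents to the assigned hemoglobin threshold". In the same section the protection at entry is put without qualification: "Randomization will be concealed, preventing allocation bias".

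The means of concealment are also described. Under sections 6.3 and 7.1 the assignment is issued only after consent, by an automated telephone system at the data coordinating center, from a list generated in advance. All screened infants are logged. The Synopsis (section 1.0) speaks only of variable block sizes and gives no numbers. The documents do not say how likely each block size is, nor that the sizes are withheld from sites.

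**The concern.** A central telephone system hides the list. It cannot hide an entry that earlier, visible assignments already determine. Short blocks of known size, run separately in each centre and weight group, produce such entries regularly.

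A prediction matters only if something before the call can respond to it, and here some steps rest on judgement. One exclusion reads "Considered nonviable by the attending neonatologist". Another turns on whether the family is likely to return for follow-up. The study team also chooses when to approach parents within the first 48 hours.

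If sicker infants were entered or held back according to the expected arm, the two groups would differ in risk from the start. The primary analysis adjusts for centre and birth weight group, which would not remove selection within those strata. Adjustment for the admission illness score is optional (section 6.10) or conditional on an observed imbalance (section 6.8). The difference that the trial is sized to detect is 7 percentage points.

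**Working it through.** The plan gives no figure for predictability, so there is none to reproduce. The check derives one.

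**Inputs**
- Block sizes 2 and 4, chosen at random, 1:1 (section 7.1). Selection probabilities are not stated. Equal probability is assumed, and the probability of a block of four, p, is varied from 0.25 to 0.75.
- 18 centres ("The NRN, with its 18 large academic medical centers, several with large satellite sites of their own", section 7.2) and two weight groups, so 36 strata.
- Total: "We will randomize 1824 infants" (section 3.3.6). The mean stratum is 1,824 / 36 = 50.7, about 51 infants.
- The observer knows the two sizes and p, does not know the size of the current block, and holds the full ordered list of past assignments in the stratum.

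**Certain assignments.** Call the arms A and B. Each finished block is balanced, so a running imbalance of two can arise only when a block of four opens AA or BB. Two of the six possible blocks of four do this (AABB and BBAA). The third and fourth entries are then certain, and no other entry ever is. So:
- expected certain entries per block = p × (2/6) × 2 = (2/3)p
- mean block length = 2(1 − p) + 4p
- long-run certain share = (2/3)p / [2(1 − p) + 4p]

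At p = 0.5 this is 0.333 / 3 = 1/9 = 11.1%.

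**Best guess.** The best strategy is to guess towards balance, and to toss a coin when the tally is level. Expected correct guesses are:
- block of two: 0.5 + 1 = 1.5
- block of four with a mixed first pair (4 of 6): 1.5 + 1.5 = 3
- block of four opening AA or BB (2 of 6): 0.5 + 0 + 1 + 1 = 2.5
- average for a block of four: (4/6) × 3 + (2/6) × 2.5 = 2.833

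At p = 0.5 the long-run hit rate is (0.5 × 1.5 + 0.5 × 2.833) / 3 = 72.2%, against 50% by chance.

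**Range over p**

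| p | Certain, long run | Infants of 1,824 | Correct guesses |
|---|---|---|---|
| 0.25 | 6.7% | 122 | 73.3% |
| 0.50 | 11.1% | 203 | 72.2% |
| 0.75 | 14.3% | 261 | 71.4% |

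**Finite strata.** Simulating a Bayesian observer in strata of 51 infants gives slightly lower shares, because the last block may be cut short. At p = 0.5 it gives 10.8% certain (about 196 infants) and 71.8% correct. At p = 0.25 and 0.75 the certain share is about 6.4% and 13.9% (about 117 and 254 infants). With equal probabilities the certain share is 9.7% in strata of 10 infants and 11.0% in strata of 100, so stratum size matters little.

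**Larger blocks.** For the same observer, with sizes 4, 6 and 8 equally likely, about 2.3% of assignments are certain (0.023 × 1,824 = 42 infants) and about 68% of guesses are correct.

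**The case against.** The strongest reply is that concealment is well built. Nobody can obtain an assignment before consent, the list sits with the data coordinating center, and block sizes vary at random. About 89% of assignments are not certain in advance. The one-in-ten figure describes an ideal observer. A real one would need an ordered list by weight group for the whole centre, including any satellites. All of this stands, and it is why the figure is an upper limit.

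A second reply is that the means to act are limited. Section 6.2 reports that all sites confirmed equipoise on the thresholds. Delay in approaching parents rarely helps, because only another entry in the same stratum changes the next assignment. Table 8 gives 3.8 to 5.7 recruits per centre per month. Split evenly over two strata, that is 1.9 to 2.85 per month. Over two days of a 30-day month, leaving siblings aside, the Poisson chance of another entry is 1 − exp(−0.127) = 12% to 1 − exp(−0.19) = 17%. This also stands, but it does not cover the exclusion judgements, which need no wait. The screening log helps only in part, since eligibility as logged already contains those judgements.

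Three stronger readings are tempting, and the documents support none of them:
- **That concealment fails.** The telephone system and the 89% of uncertain entries rule this out.
- **That a bias in percentage points can be stated.** This would need the share of centres that act on predictions and the resulting shift in risk. The documents give neither, and nothing in them suggests that sites would act.
- **That short blocks undo the independent randomization of multiples.** The natural meaning in section 7.1 is that each sibling receives its own assignment. Siblings falling in opposite arms do not bias the comparison.

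**Conclusion.** The point holds as a weakness, not as a failure of concealment. With equally likely blocks of two and four, a fully informed observer could be certain of about 11% of assignments and guess about 72% correctly. The certain share is about 7% to 14% over the range tested for the unstated block probabilities, or roughly 120 to 250 infants. These figures assume knowledge of the sizes, which section 7.1 prints, and a complete stratum tally, which will often be lacking. They measure opportunity, not bias. In a trial where caregivers cannot be masked, that is enough to make the unqualified statement in section 6.4 too strong, and the opportunity is cheap to reduce.

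**What to change.** 1. In section 7.1, delete the block sizes and refer only to variable block sizes, in line with the Synopsis. Do not print the new sizes there.
2. Have the data coordinating center use more and larger randomly chosen sizes, for example 4, 6 and 8, and record them and their probabilities only in its own randomization document.
3. In section 6.4, say that concealment reduces allocation bias.

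Steps 1 and 2 belong together. Larger blocks cut the certain share from about 11% to about 2.3%, but an observer who still knew the sizes would guess about 68% correctly, so withholding them matters as well. If enrolment has begun, sites already hold the present sizes, and deleting them without changing the list would achieve little.

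The cost is a regenerated allocation list and, if the trial has started, an amendment through the route in Appendix A (principal investigators, subcommittee, Steering Committee, monitoring committee and each local review board). The largest end-of-sequence imbalance rises from 2 to 4 infants per stratum, which is minor in strata of about 51.
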